11.6 Safety Analysis

Any adverse events, ocular or systemic, from all subjects will be utilized to summarize safety data for this study. The severity of each adverse event and the relationship of the event to the study medication will be assessed. If adverse events occur, the first concern will be the safety of the study participants. Any serious adverse event occurring during the study will be immediately reported to the principal investigator, and then to the PHRC, sub-sites, DOD, and FDA per the specified guidelines. The Research Monitor shall have the authority to stop the protocol, remove subjects from the protocol, and take any necessary steps to protect the safety and well-being of subjects until the IRB can assess the monitor's report. The monitor shall promptly report their observations and finding to the IRB or other designated official.

11.7 Interim Analysis

N/A

12. DATA AND SAFETY MONITORING

12.1 Data and Safety Monitoring Plan

A Data Safety and Monitoring Committee (DSMC) will be formed prior to trial initiation. The committee members will consist of experts in corneal disease, and the study biostatistician. In addition, [name] will function as the Medical Monitor. The Medical Monitor will provide oversight and be responsible for reporting the findings of the DSMC to the PHRC.

The DSMC will meet in an open session with select investigators prior to enrollment opening to review the protocol, objectives of the DSMC, and the plans for the DSMC throughout the course of the study. Following this open session, the DSMC will convene on an annual basis to review the data derived from the trial in a masked fashion.

The annual meeting of the DSMC will allow members to review the ongoing progress of the study and safety of the participants. From this information, the DSMC will make recommendations to the Principal Investigator and the site IRBs whether continuation of the trial is recommended.

The DSMC will review masked cumulative participant data in order to assess the integrity of the study. Specifically the DSMC will be asked to evaluate the data integrity, participant safety and scientific validity. Site summaries of patient recruitment, retention rates, data quality and completeness, protocol deviations, unanticipated events and adverse events will be shared with the DSMC to allow for a complete assessment. Data will be shared in a masked fashion with interventions coded as either A or B. If for any reason the DSMC requires unmasking of data to further evaluate safety parameters, it will be provided to them. The DSMC also can request an interim analysis if deemed necessary.

Following each meeting, the DSMC Chair, on behalf of the DSMC, will provide a recommendation to the Principal Investigator and IRB on the continuation of the study. The Committee can request continuation, modification, suspension or termination of the trial. The DSMC Chair may discuss the protocol with investigators, interview subjects, and consult with others outside the study about the research to help him reach his determination of continuation, modification, suspension, or termination of the trial.

13. DATA HANDLING, RECORD-KEEPING AND MONITORING

13.1 Data Recording, Record-Keeping and Monitoring

[name], Biostatistician will serve as the trial statistician. He will lead the data analysis for this study as well as prepare the appropriate documentation for the Data Safety Monitoring Committee meetings.

A paper (hard copy) Case Report Form (CRF) will be completed for each subject enrolled into the clinical study. The site investigators will review, approve and sign/date each completed CRF; the investigators' signature serving as attestation of the investigator's responsibility for ensuring that all clinical data entered on the CRF are complete, accurate and authentic.

All data from CRF's will be added to the study's electronic data capture system, StudyTrax. StudyTrax, a web-based electronic data capturing system, is a HIPAA and 21 CFR Part 11 compliant product that is hosted by Partners Healthcare and provides numerous academic medical centers with an electronic data capturing system to run multi-center clinical trials and other human subject research. StudyTrax will be used to collect all study data on subjects, including clinical assessments, subject medications, adverse events, as well as OCT images and Corneal Photographs. Data entered in StudyTrax are exportable to SPSS, Excel and SAS allowing for real-time data queries of enrollment, adverse event reporting.

The site investigators and research staff participating in the study are familiar with the protocol and study procedures. After each visit the CRFs will be checked by site research staff to confirm that all study procedures were completed as outlined in the protocol. Staff will also ensure that informed consents were signed at the time of enrollment and that all eligibility criteria have been met.

Source Data are the clinical findings and observations, laboratory and test data, and other information contained in Source Documents. Source Documents are the original records (and certified copies of original records); including, but not limited to, hospital medical records, physician or office charts, physician or nursing notes, subject diaries or evaluation checklists, pharmacy dispensing records, recorded data from automated instruments, x-rays, etc. StudyTrax will serve as the Source Data in addition to the Case Report Forms. When applicable,

information recorded on the CRF shall match the Source Data recorded on the Source Documents.

All study data and regulatory documentation will be monitored as outlined in the study Monitoring Plan.

13.2 Data Management

13.2.1. Identifiers

Each site will be given a unique site identification (ID) number. This number will precede each subject specific identification number to create a unique code for each participant. This code will then be included in the subject's electronic file within StudyTrax and ascribed to all data within the system to maintain subject confidentiality.

13.2.2. Confidentiality

All enrolling sites will maintain their site-specific study subject files within StudyTrax. Only appropriate study personnel at each site will be given access to StudyTrax with a unique username and password. In addition, the program allows for multiple levels of access providing added security.

The subject identification process described above allows MEEI personnel the ability to review files for data integrity and safety while maintaining the confidentiality of the study subjects.

Corneal photographs and OCT images from each site will be shared with coordinating center via secure email. All images will contain no identifiers except for the unique subject ID. The trial Image Analyst, will have access to each image through DropBox (Partners Healthcare account) allowing for confidential and masked retrieval of all study images.

Representatives from the US Army Medical Research and Materiel Command (USAMRMC) are eligible to review study records. No sensitive information is being collected for this study.

13.2.3. Disposition of Data

All subject data will be stored within StudyTrax. MEE will be the primary administrator for this study in StudyTrax. StudyTrax is hosted within a secure network. The data within StudyTrax

will be extracted at the completion of the study. This data will be held in a secure network file at MEE for at least two years following a marketing application submission to the FDA or longer, if required by the PHRC.

13.2.4. Sharing Study Results

Throughout a subject's participation in this study the investigators will be encouraged to share appropriate clinical information collected during study participation with subject's other medical care providers.

13.3 Laboratory Evaluations

A urine pregnancy test will be performed at screening (or 30 days prior to surgery). The urine collected will solely be used to evaluate levels of HCG and will not be used for other evaluations or stored for further use.

The methodology was as follows. The corneal epithelia from the enucleated eyes of mature white New Zealand rabbits were mechanically removed using a 57 blade. The corneas with 2-3mm scleral rims were excised and their irises were removed. They were fitted into Barron® artificial anterior chambers with the endothelium bathed in isotonic saline solution. The VEGA® LED-based UVA emitter was switched on for at least 30 minutes prior to calibration then was calibrated before the experiments. The corneas were then pre-treated with 0.1% riboflavin/20% dextran T500 every 2-3 minutes for 15 minutes followed by UVA light ($\lambda = 370\text{nm}$, irradiation = 3mW/cm²) at a fixed distance of 54mm from the top of the corneas for 5-minute intervals, while applying riboflavin between irradiations. Either the anterior stroma (A) or the anterior (A) and posterior stroma (P) was irradiated for different durations (7.5A, 7.5A/7.5P, 15A, 15A/15P, 30A, 30A/30P and 60A minutes). The primary control was no riboflavin/no UVA. Secondary controls included riboflavin/no UVA and UVA/no riboflavin. The corneas were trephined into 8.5-mm buttons and incubated in clean glass vials containing 0.3% collagenase A solutions at 37°C and rotating at 150 rotations-per-minute. The time to total dissolution of the corneas was measured. Each group included 4 or more corneas.

Results showed that the primary control dissolved at 4.8h ± 0.8 while tissue cross-linked for 15 minutes dissolved after 50.0 ± 8.1 hours. Compared to the control, there was a marked increase in resistance to degradation for all UVA/riboflavin cross-linked corneas. In general, anterior stromal cross-linking was superior to anterior/posterior stromal cross-linking (whether the irradiation time was split or doubled between the anterior and posterior stromata compared to their matched groups of anteriorly cross-linked corneas). The minimal treatment that yielded the greatest resistance in all groups was 15 minutes of anterior stromal cross-linking (50.0h ± 8.1 ; $p < 0.0001$). The results were similar for 15, 30, and 60 minutes of cross-linking. Therefore, we identified several methods to increase the corneal resistance to enzymatic degradation using the corneal cross-linking technique.

The UVA emitter emits constant irradiation energy of 3mW/cm² that requires the UVA light source to be at 54mm from the cross-linked cornea. The irradiated area can be controlled using

## N = 68 subjects

**Preliminary Results:** Sixty-eight Kpros were implanted in 68 eyes (56 with previous sterile corneal ulceration) in 68 patients (15 with autoimmune disease) between 2017 - 2020 across 13 sites. The average age at the time of surgery was 62 [24-89] years, 42 (62%) subjects were male and 44 (65%) were white. The mean follow-up time was 91 weeks (SD= 47.6). A total of 20 KPros were removed with an average survival time of 70 [6-160] weeks.

### Inclusion Criteria:

Previous sterile corneal ulceration	56
Autoimmune disease (ocular or other)	15
Ocular Cicatricial Pemphigoid	1
Steven Johnson's syndrome	7
Rheumatoid Arthritis	4
GVHD	2
Vogt-Koyanagi-Harada	1
Both autoimmune disease and previous ulceration	4
No autoimmune disease or previous ulceration	1

\*Will include this subject for safety analysis but will remove for efficacy analysis

### Primary endpoints or outcome measure(s)

- Time from surgery to device loss or replacement

### Secondary endpoints or outcome measure(s)

- Twelve-month retention rate
- Incidence of delayed epithelial healing at day 30 (week 4 visit)
- Time from surgery to retroprosthetic membrane treatment (laser or surgical interventions)
- Time from surgery to occurrence of vitritis (sterile or infectious)
- Time from surgery to occurrence of ocular surgery to address melt, including partial graft.
- Cornea thickness metrics measured by AS-OCT; at week(s) 1, 4, 16, 24, 36, and 52\*\*\*

### Previous KPro

- Previous KPro in the study eye: yes/no
  - If yes, how many, how long were they in the eye for and why were they removed.
  - We don't have exact dates for all previous ones since some were done at other hospitals.

Reorganize the primary and secondary outcome measures into:

- Efficacy endpoints:
  - Removal or not of the study KPro
  - Rate of retention at 52 weeks
  - Time from KPro study surgery to ocular surgery done to address a melt, including partial graft

- Safety endpoints:
  - Incidence of delayed epithelial healing at day 30 (week 4 visit)
  - Time from surgery to retroprosthetic membrane treatment (laser or surgical interventions)
  - Time from surgery to occurrence of vitritis (sterile or infectious)

We will conduct an initial analysis to examine if distributions of baseline characteristics are balanced between the two treatment groups in our randomized study. Standard descriptive statistics will be reported, median (min-max) for numerical variables and frequency count (%) for categorical variables. Comparisons of numerical characteristics between treatment groups will be conducted using the Mann-Whitney U- test. Comparisons of categorical characteristics will be conducted using Chi-square, or Fisher's exact test as appropriate.

#### Primary Analysis

The primary efficacy analysis will follow an intent-to-treat analysis strategy including all randomized eyes. The major goal of this study is to determine the efficacy of using a collagen cross-linked cornea as a carrier for the Boston Keratoprosthesis in preventing corneal melts and increasing the retention of the keratoprosthesis.

The primary endpoint of the efficacy analysis is time from surgery to device loss or replacement. Kaplan-Meier event free survival by treatment groups will be determined by the product-limit method and compared by the log-rank test to examine if survival curves are significantly different between groups. In addition, we will use a Cox proportional hazards regression model to test the effectiveness of using a collagen cross-linked cornea as a carrier for the Boston Keratoprosthesis in preventing corneal melts and increasing the retention of the keratoprosthesis. We will obtain an estimate of the hazard ratio of device loss comparing treatment with control with 95% confidence interval (95% CI). This framework allows for adjustment of baseline covariates, which may be unbalanced by chance despite the randomization of treatment assignment. The proportional hazards assumption will be assessed by examining scaled Schoenfeld residuals and log-log plots, with testing done using the “stphtest” and “stphplot” functions in Stata (version 16.0; StataCorp LLC, College Station, Texas).

If Kaplan-Meier plots of event free survival by study time, or related plots of log (-log) (survival) indicate violations of the proportional hazards assumption, then a weighted log-rank test will be used according to strategies described by Peckova and Fleming.

We will further characterize the effectiveness of using a collagen cross-linked cornea as a carrier for the Boston Keratoprosthesis by creating a composite endpoint that captures survival time until KPro removal or ocular surgery to address a melt. We will calculate the survival time of the latter by choosing the date of whichever of these two happened first as the endpoint. In doing so, we will better capture the effectiveness of using the collagen cross-linked corneas as carriers for the KPro in preventing corneal melts even for those subjects in which the melt did not warrant KPro replacement.

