11.3 Sample Size Determination

To determine the number of subjects to enroll, we performed sample size calculations based on a review of keratoprosthesis retention rates from prior studies and conservative estimates of efficacy in the treatment arm. For the control arm, we used twelve-month retention rates ranging from 50 to 60%, which has been reported in autoimmune eyes at high risk for keratoprosthesis loss. Therefore, we anticipate the twelve month retention rate for the untreated (not cross-linked) cornea will be 50-60%. To estimate the retention rate in the treatment arm, we reviewed the retention rates from the two published case reports that describe cross-linking of the keratoprosthesis carrier cornea in high-risk eyes (Kanellopoulos et. al. & Robert). While the two case reports describe a 100% retention rate in a total of 12 eyes at one year, the exact retention rate for a multicenter study is not known. Using a two-sided log rank test for equality of survival curves, we performed sample size calculations so that we could detect a 30% difference in retention rate between the treatment group and the control group and specified the probability of type 1 error of 0.05, a study power of 80%, a follow up period of twelve-months, and a 4% loss to follow up. In order to detect a difference between the control arm and the treatment arm using

these considerations, the calculations resulted in sample size estimates between 82 and 88 subjects (Table 2). For practical purposes, we also took into consideration the time available for the study and the number of high risk keratoprosthesis procedures performed at each study site. Using the mid-range estimates, we aim to enroll 84 subjects into this study.

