11.5 Effectiveness Analysis

We will conduct an initial analysis to examine if distributions of baseline characteristics are balanced between the two treatment groups in our randomized study. Standard descriptive statistics will be reported, median (min-max) for numerical variables and frequency count (%) for categorical variables. Comparisons of numerical characteristics between treatment groups

will be conducted using the Mann-Whitney Wilcoxon test. Comparisons of categorical characteristics will be conducted using Chi-square, or Fisher's exact test as appropriate.

Primary Analysis

The primary efficacy analysis will follow an intent-to-treat analysis strategy including all randomized eyes. The major goal of this study is to determine the efficacy of using a collagen cross-linked cornea as a carrier for the Boston Keratoprosthesis in preventing corneal melts and increasing the retention of the keratoprosthesis. The primary endpoint of the efficacy analysis is time from surgery to device loss or replacement. Kaplan-Meier plot of event free survival by treatment groups will be provided and log-rank test will be used to examine if survival curves are significant different between groups. In addition, we will use a proportional hazards regression model to test the effectiveness of using a collagen cross-linked cornea as a carrier for the Boston Keratoprosthesis in preventing corneal melts and increasing the retention of the keratoprosthesis. We will obtain an estimate (95% CI) of the hazard ratio of device loss comparing treatment with control. This framework allows for the control of covariates, which may be unbalanced by chance despite the randomization of treatment assignment. If Kaplan-Meier plots of event free survival by study time, or related plots of log (-log) (survival) indicate violations of the proportional hazards assumption, then weighted log-rank test will be used according to strategies described by Peckova and Fleming.

Secondary Analysis

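### The plot-triggered move from log-rank to weighted log-rank is uncalibrated, so the two-sided 5% level of the primary test is not guaranteed

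*SAP*

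**What the plan says.** Under Primary Analysis, the SAP compares time from surgery to device loss or replacement by the log-rank test, with a Cox model for the hazard ratio. Proportional hazards are to be examined by scaled Schoenfeld residuals and log-log plots, with a formal Stata test (stphtest) but no significance level for it. A separate sentence then says that if by-arm Kaplan-Meier or log(-log) plots "indicate violations of the proportional hazards assumption, then a weighted log-rank test will be used", following strategies from a cited paper.

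Protocol 11.5 has the same rule: "then weighted log-rank test will be used according to strategies". The title of the cited paper (Protocol reference 14) describes an adaptive test for a difference in survival distributions.

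The error level appears only in Protocol 11.3, where it belongs to the log-rank test: "Using a two-sided log rank test for equality of survival curves", the sponsor "specified the probability of type 1 error of 0.05, a study power of 80" percent. The SAP does not restate it. Neither document says which p-value decides if both tests are run.

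**The concern.** Which test decides the primary comparison depends on how the two arms' curves look, and those are the curves being tested. A rule of this kind keeps its error rate only if the trigger, the replacement statistic and the critical value are fixed together. Here the trigger is a reading of plots with no threshold, the weight is left to a citation, and no critical value is given.

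Validity does not require the switch. Under the null hypothesis the two curves are identical, so the hazard ratio is 1 throughout and the log-rank test has its nominal size. Non-proportional hazards affect its power and the meaning of the Cox hazard ratio, not its false-positive rate.

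At stake is the credibility of a borderline result. The SAP reports 20 removals in 68 eyes. If the weighted test gave a p-value just under 0.05 and the log-rank one just over, a reader could not tell whether the plan or a judgement about a plot had decided the outcome.

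**Working it through.** **1. Which test the trial was sized on.** Inputs from Protocol 11.3: "we used twelve-month retention rates ranging from 50 to 60" percent in controls; "detect a 30% difference in retention rate between the treatment group and the control group"; "a study power of 80%, a follow up period of twelve-months, and a 4% loss to follow up"; two-sided 0.05.

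Freedman's log-rank formula, with HR = ln(p2)/ln(p1): events = (1.960 + 0.842)² × [(1 + HR)/(1 − HR)]². For 0.55 against 0.85:

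- HR = 0.1625/0.5978 = 0.272
- events = 7.85 × (1.272/0.728)² = 23.9, rounded up to 24
- N = 24/0.30 = 80; 80/0.96 = 83.3, rounded up to **84**

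The other two rows give 90 and 80, against the stated 88 and 82. The chosen 84 is reproduced, so the design figure belongs to an unweighted log-rank test.

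**2. Rule simulated under no treatment effect.** The weighted statistic is Z_w = Σ w(t)(observed − expected) / √[Σ w(t)² × variance], with w = 1 for the log-rank, S for early, 1 − S for late and S(1 − S) for middle differences, where S is pooled survival. If a scaled-Schoenfeld trend test is significant at the trigger level, reject when |Z_w| > 1.96; otherwise reject when the log-rank |Z| > 1.96. The documents give neither trigger level nor weights. Assumed ranges: triggers of 5, 10, 20 and 30%; the three weights above, or early/late chosen from the data.

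- Scenario A (SAP results): 68 eyes; follow-up uniform on 8.5 to 173.5 weeks, which has mean 91 and SD 165/√12 = 47.6 as reported; hazard 0.0040 per week. Expected events = 68 × {1 − [e^(−0.034) − e^(−0.694)]/0.66} = 19.9.
- Scenario B (protocol design): 84 eyes; pooled 12-month retention (0.55 + 0.85)/2 = 0.70; about 12 months of follow-up; 25.6 events on average.

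With 100,000 trials per scenario (Monte Carlo SE 0.07 points), the type I error is:

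| Rule | A | B |
|---|---|---|
| Log-rank always | 5.0% | 4.9% |
| Switch to early weight | 5.1% | 4.9–5.0% |
| Switch to S(1 − S) weight | 5.6–6.3% | 5.4–6.0% |
| Switch to late weight | 5.8–6.6% | 5.6–6.2% |
| Switch to early or late, picked from the data | 6.1–7.8% | 5.8–7.3% |
| Any of the four tests, no trigger (outer bound) | 8.5% | 7.9% |

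The early-weighted statistic correlates 0.99 with the log-rank, so switching to it changes almost nothing. The late-weighted one correlates 0.82 (A) and 0.85 (B), which leaves room for inflation.

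**3. Would a sound adaptive replacement cure it?** Suppose the replacement is a maximum-type adaptive test calibrated to 5% when always used. Used only after the trigger, the whole rule gives 5.8–6.3% (A) and 5.6–6.1% (B); in that run the log-rank alone gave 5.2% and 5.0%. The excess of roughly 0.6 to 1.1 points comes from using the replacement only when the curves look non-proportional.

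**4. A rule that holds.** The largest of the log-rank, early-weighted and late-weighted |Z|, always applied with its own critical value (2.18 in A, 2.15 in B), has size 4.9% and 5.1% in 40,000 separate trials each.

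**5. Sensitivity.** With 68 eyes and about 17 events: fixed log-rank 4.7%, early weight 4.7–4.8%, late 5.6–6.5%, picked from the data 5.8–7.6%, outer bound 8.2%. With 67 eyes (68 less the one the SAP drops from efficacy) and 20/(68 × 91) per week = 0.168 per year: fixed log-rank 5.2%, picked from the data 6.1–7.5%, outer bound 8.3%.

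**The case against.** The rule is in the protocol and repeated in the SAP, so it is prespecified. It points to a published strategy whose title describes an adaptive test, and that strategy may fix the weights and control its own error. The SAP also commits to a formal proportional-hazards test alongside the plots. The trial is phase I/II, and the likely inflation is small.

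Most of this stands as a limit on the point. A reader might infer a post hoc change of test, or an analyst free to take any weight; the documents support neither. The choice is delegated to a cited method whose content they do not give, so the simulated weights are assumptions. The SAP says the weighted test will be used without saying that the log-rank result is set aside; replacement is the natural reading, but it is not explicit.

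The objection does not remove the problem. Prespecifying a data-dependent choice does not calibrate it, and step 3 shows some excess even with a replacement that is valid in its own right. The formal diagnostic has no level, and the switching sentence names only the plots.

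**Conclusion.** The point holds in a limited form: the conditional rule is uncalibrated, so two-sided 5% is not guaranteed for the primary comparison. Under the assumed triggers and weights, the inflation runs from about 0 points (fixed early weight) to about 3 points (early or late weight picked from the data). The actual size cannot be computed, because the trigger and the weight are not written down and the simulated pre-test stands in for a visual judgement.

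Two stronger readings are tempting. One is that the 5% level is broken outright; the early-weight case shows that it need not be. The other is that the error rate is about 8%. That figure needs free choice among all tests with no trigger, which the plan does not allow. Nor do the documents give any figure for how often plots based on about 20 events would mislead.

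**What to change.** In the SAP, name one confirmatory primary test at two-sided 0.05, applied whatever the proportional-hazards diagnostics show. Either choice is sound:

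- the log-rank test, on which the trial was sized; or
- if protection against early or late effects is wanted, a fixed combination of log-rank, early-weighted and late-weighted statistics, with the weights written out and a joint critical value (about 2.15 to 2.18 in these scenarios, to be derived for the final design).

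Replace the switching sentence accordingly. Keep the Cox hazard ratio as the estimate, and use the Schoenfeld test and plots to judge how to interpret it. Report weighted log-rank tests with pre-named weights, and survival differences at fixed times, as supportive only. Align Protocol 11.5 if it is amended.

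The cost is a sentence or two of text. The log-rank choice loses some power if the effect is strongly delayed; the combination test pays with a critical value slightly above 1.96.
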